Participants will be asked to give a baseline salivary sample (5ml over 5 minutes) and then asked to rinse with an unlabeled (blinded) antiseptic mouth rinse for 60 seconds according to the table below. The rinses and control will be similar in appearance visually, such that a double-blind can be maintained. The research assistant ([name]) will be the sole unblinded staff member who will perform randomization and communicate the subject's group assignment to blinded study staff, in advance of the visit based on the block randomization schedule. The unblinded staff member will set-up the rinses for the participants appointment minimizing the possibility of study staff being able to identify the blinded rinses. In the instance that [name] is unavailable, [name] or [name] will perform randomization and set-up the rinses. Blind will be strictly maintained except in the case of medical emergency requiring reveal of an individual's rinse identity. The product group key will be provided to the analyzing statistician at the conclusion of the clinical study.

mouth rinse*	Number of participants (sample size)	Group
26.9% ethanol plus essential oils	84	Experimental
0.1% Cetylpyridinium Chloride	84	Experimental
Sterile water	84	Control

**All mouth rinses are commercially available in the USA, routinely used in clinical settings, and will be used in an on-label manner.*

After the participant expectorates the mouth rinse, research staff will collect another salivary sample (T_0 , 2 mL over 5 minutes). During a 10 minute recuperation period, the study participants will answer demographics survey questions and questions regarding the taste, color, flavor and general acceptability of using the mouth rinse as part of routine dental and medical visits as well as in social settings. At 15 minutes post-rinse, the participant will be asked to provide an additional saliva sample (2 mL over 5 minutes), followed by another 10 minute recuperation period. This sequence will be repeated for at

the 30, 45 and 60-minute time points post rinse. At 60 minutes, the study participant will give their final salivary sample (2 mL over 5 min), and study participation will conclude.

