- Patient with developmental/cognitive disability that cannot self-consent, comprehend and follow the requirements of the study based on research site personnel's assessment.
- Patients with sizable mucosal tears, abrasions, growths or burns in the mouth
- The following table lists exclusion criteria specific to each mouth rinse proposed in the study:

mouth rinse*	Exclusions
26.9% ethanol plus essential oils	
 ● Do not use in children under 12
0.1% Cetylpyridinium Chloride	
 ● Do not use in children under 6
Sterile Water	No contraindications

**All mouth rinses are commercially available in the USA, routinely used in clinical settings, and will be used in an on-label manner.*

Summary of Inclusion and Exclusion Criteria for Mouth rinse RCT

Inclusion Criteria	Exclusion Criteria
Individuals (all sex, all gender) at least 18 years of age and at most 65 years of age in good oral health and with stable physical health, decided at the discretion of the study coordinator.	Known allergies or significant adverse reactions following the use of oral hygiene products (toothpastes, mouth rinses), commercial cosmetics, iodine, and any ingredient in the mouth rinses (list will be provided).

Diagnosed COVID+ status by physician, official testing site, or on-site rapid antigen test administered by study personnel at the time of visit. Either became symptomatic or initially tested positive in the prior 10 days.
	
Established history of severe Xerostomia (drug-induced or autoimmune dry mouth), severe periodontal disease with actively bleeding gums, significant oral abrasions/ulcers or growths, alcohol abuse, and/or recreational drug abuse. Other severe acute or chronic medical or psychiatric condition or laboratory abnormality that may increase the risk associated with trial participation or investigational product administration or may interfere with the interpretation of trial results and, in the judgment of the Investigator, would make the subject inappropriate for entry into this trial.

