6.2.1 Screening Evaluation

Consenting Procedure

Patients will be contacted first by phone and, if not available, then by email. The consent process will be conducted by a study coordinator. The study's purpose and requirements will be explained and the patient will have the opportunity to ask questions and will have time to consider participation. Interested patients will make an appointment to visit the Go Health Clinical Research Unit at Adams School of Dentistry for this study. Study participation includes only one visit. The consent forms will be reviewed and signed by interested patients in person in the clinical isolation unit associated with the Go Health Clinical Research Unit at Adams School of Dentistry prior to study participation. For Spanish speaking patients and/or parents, Spanish forms will be provided and

communication will occur through a Spanish translator. For hospital in-patients appearing on the EPIC COVID+ list, subjects will be approached by a study coordinator in their private room. The study's purpose and requirements will be explained and the patient will have the opportunity to ask questions and will have time to consider participation. If interested, consent forms will be left in the patient's room for review. Study team members will return later for final consent signatures and if consenting, the study visit can occur in their hospital room. All patients are adults and have normal cognitive capacity, and therefore will be able to consent for themselves.

Screening

PreScreening is typically done through a phone call but may be supplemented with email correspondence. The screening process is finalized at Visit 1.

- During the prescreening conversation the patient will answer screening questions regarding inclusion and exclusion criteria and will be provided with the informed consent to read and review prior to consenting and enrollment process.

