9.2 Sample Size and Randomization

Based on similar viral infectivity studies evaluating antiviral mouth rinse efficacy, we were able to run power calculations to estimate effect size and determine sample size as a function of length of mouth rinse time course. The sample size is justified by a paired t-test on outcomes between time points. With simultaneous comparisons, the sample size n=43 for each mouth rinse can detect the effect size in Cohen's $d = 0.8$ at 30 minutes, which is between medium and large, under 80% power and 0.016 type-I error rate by Bonferroni correction.¹² To account for 14% of patients having no virus in their saliva and 10% of patients producing insufficient saliva, we plan to enroll 55 participants per arm.

The statistical consultant on this project will create a block randomization tool for the study staff; the unblinded staff member will randomize a participant once enrollment compliance has been confirmed and consent has been given. The participant's group assignment will then be communicated to the blinded study staff. IRB approved study personnel will ask participants screening questions to confirm eligibility for enrollment. After consent and screening, the randomization tool will be used by study staff to assign the subject to a study group.

The researcher responsible for collecting the salivary samples will be blinded to the mouthwash solution, as they will be given a pre-aliquoted mouth rinse in an unlabeled tube to provide to the patient for the rinse.

The PI, Co-I, study coordinators and study personnel who work for GoHealth are authorized to break the blinding based on emergency medical necessity such as if a patient suffers an allergic or adverse reaction to one of the mouth rinses. Though highly unlikely as all mouth rinses are sold commercially at Walgreens and CVS, adverse or allergic reactions are possible. Using the numerical code associated with the participant and mouth rinse syringe, the study personnel responding to the emergency can reference the block randomization schedule to determine the mouth rinse type, to inform the emergency medical workers, poison control or the emergency room what type of mouth rinse product led to the reaction.

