10.2 Data Management

An Excel key will be created by the study coordinators with study ID (random alphanumeric code) to identify patients, saved in a secure folder on a UNC SOD server. This linkage file will be stored separately from data and destroyed at the close of the study and will never be shared beyond the study coordinators.

All data collected from participants and results from sample analysis will be coded with unique numerical identifiers and stored in the UNC CDART clinical research database and on a secure UNC-CH server. Only trained, IRB-approved study personnel will enter and access data in the secure CDART research database.

Consented patients' data (including screening questions, demographics, and the survey on mouth rinse acceptability) will be collected using the CDART dental toolkit program, which stores data on a secure UNC maintained server and meets federal guidelines for clinical study data acquisition. Only HIPAA and human subjects trained, IRB-approved study personnel will collect, enter and manage patient data; study coordinators will serve in this capacity.

Data will be collected in the CDART research database using participant's study ID and no other PHI identifiers, on approved, carefully designed digital forms within CDART. CDART forms will include questions with drop downs, radio button multiple choice and text field entry, depending on the question type. There will be separate digital forms for inclusion/exclusion screening questions (before sample collection begins), demographic

questions, and questions regarding mouth rinse experience (taste, color, sensation) and willingness to use a mouth rinse in various settings (e.g. dentist or doctor appointments). A separate linkage file, securely stored on UNC servers, will be utilized to associate the random alphanumeric study ID with patient identifier, so samples and CDART data will not be associated with patient identifiers.

Data will only be transmitted among the research team using the SOD secure research server. Demographic data will be transmitted among the research team through access to the secure CDART research database system, stored on secure UNC servers, which study personnel will access only through encrypted computers via secure user account.

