11.3 Participant Confidentiality

An Excel Linkage File key will be created with study ID (random alphanumeric code) to identify patients, saved in a secure folder in a UNC School of Dentistry (SOD) server, by the unblinded staff member. This linkage file will be stored separately from data and destroyed at the close of the study.. All data collected from participants and results from sample analysis will be coded with unique numerical

identifiers and stored in the UNC CDART clinical research database and on a secure UNC-CH server. Data will only be transmitted among the research team using the SOD secure research server. Demographic data will be transmitted among the research team through access to the secure CDART research database system, stored on secure UNC servers, which study personnel will access only through encrypted computers via secure user account. All research personnel will be trained in maintaining patient confidentiality and HIPAA.

Any data, specimens, forms, reports, and other records that leave the site will be identified only by a participant identification number (Participant ID, PID) to maintain confidentiality. We do not anticipate any data, specimens, forms reports and other records leaving the site as sample storage and analysis will occur on site. All paper records will be kept in a locked file cabinet, and all digital records will be stored in the encrypted, secure, password protected CDART research database. All computer entry and networking programs will be done using PIDs only. Information will not be released without written permission of the participant, except as necessary for monitoring by IRB, the FDA, the NCCIH, and the OHRP.

There is little to no potential for deductive disclosures from the survey portion of this study. Patients will be asked about the experience rinsing with a commercially available mouth rinse (such as Listerine). They will be asked to rate the taste, appearance/color, sensation, and their willingness to use the mouth rinse in the future. General demographics will be asked such as gender, race, ethnicity and age bracket. Their identity cannot be deduced from this information.

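### The plan contradicts itself on whether assignment comes before or after consent and eligibility, and does not secure allocation concealment

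*Combined protocol and SAP*

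**What the plan says.** All references are to the combined protocol and SAP.

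- **Section 3 (Study Design).** One research assistant "will be the sole unblinded staff member who will perform randomization" and passes on the subject's "group assignment to blinded study staff, in advance of the visit", working from the block schedule. Two named stand-ins cover absence.
- **Section 6.2.1.** "The consent process will be conducted by a study coordinator". Outpatients sign in person at the single visit, and screening is completed there (consent also in Section 4.3).
- **Section 4.2, summary table.** Whether a volunteer is in good oral health and stable physical health is "decided at the discretion of the study coordinator".
- **Sections 4.3, 6.2.2, 9.2 and 11.2.** Consent and eligibility screening come before assignment.
- **Section 9.2.** The tool is made for study staff. The unblinded staff member randomises once eligibility and consent are settled. Then, after consent and screening, "the randomization tool will be used by study staff to assign the subject to a study group".
- **Section 9.2, last paragraph.** The PI, Co-I, study coordinators and GoHealth personnel may break the blind in a medical emergency by looking up the participant's code in the block schedule.

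No section gives the block size, says where the schedule is kept, or says how later assignments are hidden from the people who enrol.

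**The concern.** Randomisation makes the three arms comparable only if the person deciding on entry cannot know the coming assignment. Section 3 puts the assignment in circulation before that decision is made. Two things follow.

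First, someone can be assigned and then fail at the visit: a negative on-site antigen test, a positive pregnancy test, or the coordinator's judgement on health. Such a person has used a place in a block. Section 9.3 describes who may join the study and does not say how that person would be counted.

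Second, if the assignment or its code reaches the people running the visit beforehand, the discretionary criterion can be applied with that knowledge. Blinding the saliva collector and the laboratory protects measurement but not selection. The ANCOVA in Section 9.5, if it adjusts for baseline titre, removes only the part of a selection difference that the baseline titre explains.

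**Working it through.** There is no figure in the plan to reproduce. The check is a comparison of the text, followed by an illustration of size.

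**Order of events**

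| Step | Section 3 | Sections 4.3, 6.2.2, 9.2, 11.2 |
|---|---|---|
| Assignment passed to blinded staff | Before the visit | Only after the two steps below |
| Consent signed | At the visit (4.3, 6.2.1) | Before assignment |
| Eligibility settled | At the visit (6.2.1) | Before assignment |

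For an outpatient, consent and final screening happen at the visit. Assignment passed on before the visit therefore precedes both, and the two columns cannot both be followed.

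**Access to the schedule.** The emergency route in Section 9.2 uses the block schedule itself. A person who opens it to find one participant's rinse can also see the assignments that follow. The roles allowed to do this include the coordinators, who obtain consent and judge one eligibility item.

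**Chance of knowing the next assignment** (three equal arms, 84 each in Section 3)

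- Fully concealed: 1/3 = 0.33.
- Assignment or schedule visible: 1.00.
- Only the earlier assignments in a fixed block known: at each position the best guess is the arm with most places left, right with probability (largest number left)/(total left). Average this over all positions and block orders.
  - Block of 3: (1/3 + 1/2 + 1)/3 = 0.611.
  - Block of 6: (0.333 + 0.400 + 0.500 + 0.533 + 0.600 + 1.000)/6 = 3.367/6 = 0.561.
  - Blocks of 9 and 12, by the same recursion: 0.532 and 0.512.

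These block sizes are assumed. If staff see only group codes, the figures apply to guessing the next code, which matters once a code has been linked to a rinse.

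**Illustration of bias.** Assume a fraction f of one arm is steered and those people differ by δ SD on the analysed outcome. The arm mean shifts by f × δ. With δ = 1, f = 10% gives 0.10 SD and f = 20% gives 0.20 SD. With δ = 0.5 the shifts are 0.05 and 0.10 SD. For a two-sided 5% two-sample t-test with no true effect, the noncentrality is shift × √(n/2). Both arm sizes in the documents are used: 84 (précis, Section 3) and 55 (Sections 2.2, 9.1, 9.2, 9.5).

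| n per arm | Shift (SD) | Noncentrality | Rejection rate |
|---|---|---|---|
| 84 | 0.05 | 0.05 × 6.48 = 0.32 | 0.062 |
| 84 | 0.10 | 0.10 × 6.48 = 0.65 | 0.099 |
| 84 | 0.20 | 0.20 × 6.48 = 1.30 | 0.252 |
| 55 | 0.10 | 0.10 × 5.24 = 0.52 | 0.081 |
| 55 | 0.20 | 0.20 × 5.24 = 1.05 | 0.180 |

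**The case against.** The best defence is that four sections state the right order and only Section 3 departs from it. The early message may be a practical step, so that an unlabelled rinse is ready on arrival, and since the recipients are meant to stay blinded it may be only a code. The sentence in Section 9.2 about study staff opens by placing itself after consent and screening. Section 6.2.2 gives the tool to the unblinded staff, and Section 11.2 has the unblinded staff member randomise. On that reading, study staff is a loose term for the unblinded person.

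Much of this stands. A reader might infer that coordinators hold the tool, but no section says so. The word sole is qualified by the stand-ins in the same paragraph, which is ordinary cover. A reader might also infer that the unblinded person is a coordinator, because Section 11.3 has the name-to-ID file created "in a UNC School of Dentistry (SOD) server, by the unblinded staff member" while Section 10.2 has the coordinators create it and says it "will never be shared beyond the study coordinators". That is a genuine mismatch, but the file is a confidentiality key, not the allocation list, and Section 3 calls the unblinded person a research assistant.

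The motive to steer is also limited. The trial is one visit, does not treat COVID-19, and measures a change within about an hour. Emergency look-ups should be few: Section 2.2 puts allergy below 1%, so fewer than 0.01 × 252 = 2.52 cases would be expected even if all arms counted.

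Two things are not answered. The defence does not remove the contradiction in Section 3, which would assign people before eligibility is settled. And it does not supply any statement of how later assignments are hidden.

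**Conclusion.** The point holds as a contradiction in timing together with a gap in concealment. Section 3 conflicts with Sections 4.3, 6.2.2, 9.2 and 11.2 on when assignment happens. Section 9.2 is loose about who uses the tool, and its emergency route opens the whole schedule to people who also enrol. This should be corrected, because following Section 3 as written would put assignment ahead of consent and eligibility.

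A reader might go further and conclude that enrolling staff will know the next assignment, or that the comparison with water will be biased by a stated amount. The documents support neither. The certainty of 1.00 applies only to someone who sees the assignment or the schedule. The 51% to 61% range rests on assumed fixed blocks. The error rates of 6% to 25% rest on an assumed 10% to 20% of one arm being steered and an assumed 0.5 to 1 SD difference. They show what concealment guards against and are not estimates for this trial.

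**What to change.** 1. In Section 3, remove the timing at the end of "group assignment to blinded study staff, in advance of the visit". State, in line with Sections 4.3, 6.2.2, 9.2 and 11.2, that assignment is generated and communicated only after consent and eligibility are recorded in CDART.
2. In Section 9.2, replace both mentions of study staff as users of the tool with the unblinded staff member or a named stand-in. State that whoever opens the tool for a participant does not consent, screen or sample that participant.
3. Have the tool release one assignment at a time, with later ones hidden. Keep the block sizes, preferably varying, from enrolling staff.
4. Have emergency unblinding show only the affected participant's code, not the schedule.
5. As a clerical matter, reconcile Sections 10.1 and 10.2 with Section 11.3 on who creates and keeps the linkage file.

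The cost is protocol wording and a setting in a tool that the statistician is already to build. No extra participants or assays are needed. Rinse set-up moves into the visit and adds a few minutes, and cover must come from staff who are not enrolling that participant.

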6.2.3 Blinding

At their onsite visit, subjects will be provided with an unlabeled/blinded mouth rinse. The researcher in charge of collecting the salivary samples will be blinded to the mouthwash solution as well, as they will be given a pre-aliquoted mouth rinse in an unlabeled storage syringe to provide to the patient for the rinse. Our statistical consultant, [name], will set up a randomization schedule that the team will abide by for assignment of enrolled subjects.

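### Emergency unblinding by looking in the block randomisation schedule could show other and future assignments to staff who also take consent and judge eligibility

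*Combined protocol and SAP*

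**What the plan says.** **Who is unblinded in routine work.** Section 3 names one research assistant who "will be the sole unblinded staff member who will perform randomization", with two named back-ups. Section 6.2.2 says the block randomisation tool goes to that unblinded staff member.

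**When the blind may be broken.** Section 3: "Blind will be strictly maintained except in the case of medical emergency". The same sentence limits the disclosure to the rinse given to the person concerned.

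**Who may break it, and how.** Section 9.2: "The PI, Co-I, study coordinators and study personnel who work for GoHealth are authorized to break the blinding based on emergency medical necessity". Starting from the number that links participant and syringe, "the study personnel responding to the emergency can reference the block randomization schedule to determine the mouth rinse type".

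**When the schedule is made.** Section 6.2.3 says the statistical consultant "will set up a randomization schedule that the team will abide by for assignment of enrolled subjects", and Section 4.3 likewise has the statistician create the block schedule.

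**Who controls entry.** Section 6.2.1: "The consent process will be conducted by a study coordinator". Section 9.2: "IRB approved study personnel will ask participants screening questions to confirm eligibility for enrollment". The summary table of criteria in Section 4.2 leaves the judgement of stable physical health to the study coordinator.

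**The concern.** A code break should disclose one assignment and nothing else. Section 9.2 instead makes the allocation list itself the emergency tool, and the staff who may consult it include those who recruit. If a coordinator has seen the coming assignments, the decision to approach or accept a borderline candidate, or the timing of a visit, can depend on the rinse that comes next. Allocation concealment exists to prevent that, and the comparability of the three arms rests on it.

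Decisions after assignment are open to the same influence. Sections 6.2.5 and 8 let the investigator discontinue a participant on judgement, and they remove and replace participants with too little saliva. Section 10.1 has study personnel put the survey questions and enter the answers, so staff who knew the rinse could also colour the acceptability data.

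**Working it through.** The plan gives no figure for this point, so the check is mainly a comparison of sections.

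**1. Is the schedule fixed ahead of enrolment?** Yes. Sections 4.3 and 6.2.3 have the statistician prepare it, and participants are then placed on it. At any time before the last enrolment it contains assignments not yet made.

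**2. Do the people who may consult it overlap with the people who recruit?** Yes, for coordinators. They are on the Section 9.2 list, they run consent (6.2.1), they approach in-patients (4.3), and they make one discretionary eligibility judgement (summary table, 4.2).

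**3. Is the look-up confined to one record?** Not by anything written. The search starts from one participant's number, but it is made in the schedule. The plan describes no sealed card, single-record display, access log or rule on where the schedule is kept.

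**4. Could coded group labels prevent the exposure?** Section 3 sends the product group key to the statistician at the end of the clinical study, so the labels may be coded. But Section 9.2 says the schedule identifies the rinse type. If a label were shared by a whole group, decoding it once would unmask every member of that group.

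**5. Does Section 9.2 deliver the limit in Section 3?** From steps 1 to 4, it does not secure it.

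**How likely is a look-up?** This is context only. Section 2.2 gives allergy as under 1% and no other rate. Assume each participant on an active rinse triggers a look-up with probability p, independently. Then

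P(at least one) = 1 − (1 − p)^N.

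N is 2 × 84 = 168 from the Section 3 table, or 2 × 55 = 110 from the 55 per arm in Section 9.2. The two enrolment figures differ, so both are shown.

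| p (assumed) | N = 168 | N = 110 |
|---|---|---|
| 1% (ceiling) | 1 − 0.99^168 = 82% | 1 − 0.99^110 = 67% |
| 0.5% | 1 − 0.995^168 = 57% | 1 − 0.995^110 = 42% |
| 0.1% | 1 − 0.999^168 = 15% | 1 − 0.999^110 = 10% |

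**How much could one look-up show?** If it falls at a random position among T enrolments, the mean number still to come is (T − 1)/2. For T = 3 × 84 = 252 this is 251/2 = 125.5. For T = 3 × 55 = 165 it is 164/2 = 82. These are upper figures: they suppose that the whole list is in view and that the viewer reads and retains it.

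**The case against.** The strongest reply is that a reader might infer far more than the text says.

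- **Standing access.** A reader might conclude that all GoHealth staff can open the list at will, so that all 252 assignments are known from the start, against one in three by chance. The documents do not say this. Section 9.2 permits access only in an emergency, Section 6.2.2 gives the tool to the unblinded staff member, and routine custody is not stated. Full predictability is a worst case.
- **Layout.** The look-up is keyed to one participant, and the form of the schedule is not described. That a single look shows the whole list is a possibility, not a stated fact.
- **Loss of blinding throughout.** A reader might infer that blinded sample collection fails for everyone. It does not. Samples taken before a look-up were collected blind, and collectors receive unlabelled containers. Section 3 has the laboratory work from alphanumeric labels only, so the primary assays stay masked.
- **Contradiction between sections.** Section 3 itself foresees the emergency exception, so the two sections do not conflict on whether unblinding may happen. They differ on how much it discloses.
- **Rarity.** Section 9.2 regards reactions as very improbable, and Section 9.4 expects adverse outcomes to be extremely rare. The 82% needs both the ceiling rate and a look-up after every reaction. On the other side, the trigger in Section 9.2 covers adverse reactions as well as allergy.
- **Order of steps.** Sections 4.3, 6.2.2, 9.2 and 11.2 place consent and screening before assignment. This limits selection but does not remove it if the next slot is known. Section 3 also has the assignment passed on ahead of the visit, which fits poorly with that order.
- **Overlap of roles.** Names are removed, so it cannot be seen whether the back-ups are themselves coordinators. The overlap for coordinators as a role stands regardless.

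These replies reduce the size of the problem. They leave the gap itself: the stated method has nothing that confines it to one participant.

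**Conclusion.** The point holds as a weakness in the emergency mechanism, worth correcting because the correction is cheap. It does not show that concealment has failed or will fail. It rests on two things the text supports, a schedule prepared in advance and a role that both recruits and may consult it, and on the absence of any described restriction, custody rule or log.

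Harm is conditional on a real emergency look-up, or on the schedule being kept within these staff members' reach. The chance of at least one look-up ranges from 10% to 82% across the assumed rates and the two enrolment figures, with 82% and 67% as ceilings. If the list were fully visible, about 125 later assignments on average could be seen at 252 enrolled, or 82 at 165. What is exposed is allocation concealment and staff blinding for later participants.

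**What to change.** Reconcile Sections 3 and 9.2 as follows.

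1. State that the schedule is held only by the statistician and the designated unblinded staff, and where it is kept.
2. Replace the schedule look-up with a single-participant code break: a sealed card for each study ID, or a restricted, audit-trailed field in CDART that shows one participant's rinse.
3. Log each use with the date, reason and role of the person.
4. Make the code known to blinded staff unique to the participant and not a shared group label, so that one reveal does not decode a whole arm.

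Who may unblind and in what circumstances stays as written, and emergency access remains immediate. The cost is one database field, or a set of cards: 252 at the larger enrolment figure, plus one for each replacement under Sections 6.2.5 and 8, whose number the plan does not give.
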